All clinically relevant radiologic images will be transferred to the Radiation Oncology Pinnacle (Philips, Cleveland, OH) treatment-planning system. Using the various MRI sequences and the CT image data sets, a composite gross tumor volume (GTV) will be generated. The focal GTV will be contoured and approved by the attending radiation oncologist and urologist. The 4D CT will be fused with the treatment planning CT and an internal target volume (ITV) will be generated. The location of tumor foci from each positive biopsy core will also be segmented and expanded by 5mm to add to the PTV along with imaging data sets. An additional 0.3-0.5 cm margin will be placed around the image data set ITV to generate a final PTV to account for set-up variation. The use of abdominal compression may be used to decrease the volume of ITV since there is no real-time target tracking. Surrounding normal structures, including the rectum, small bowel, bladder, femora, seminal vesicles, penile bulb, and skin will be contoured. Skin is defined as a 0.5 cm concentric ring beneath the skin.

Mid Treatment and Post SBRT (MRI) with multiparametric sequences (mpMRI)

Each subject will be offered up to 4 additional MRI scans: 1 during therapy (between the 2nd and 3rd fractionated treatments), at 6 months following the end of radiation therapy, and again at 12 and 24 months. All mpMRI will be requisitioned in the same manner as described above (Staging MRI) as described above at page 16 (6.1 Imaging the Prostate), with the exception that contrast with gadolinium is preferred. If patients are unwilling or clinically unable to undergo contrast or have all follow-up MRI scans, the patient will remain on study and followed for PSA response and toxicity outcomes.

Computed Tomography (CT)

CT will be fused with MRI scans and used as a primary image platform for treatment planning. It is preferred that CT with contrast be acquired, unless clinically contraindicated. The simulation should be performed in the supine treatment position, in the custom made immobilization device, with the fiducial markers and rectal balloon in place (where utilized). Axial cuts of 2.0 mm or less will be acquired throughout the pelvis and prostate from the top of the iliac crests superiorly to the perineum inferiorly.

Contrast

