Evaluable Non-Target Disease Response Patients who have lesions present at baseline that are evaluable, but do not meet the definitions of measurable disease, have completed a course of SBRT, and have had their disease re-evaluated by imaging will be considered evaluable for non-target disease. The response assessment is based on the presence, absence, or unequivocal progression of the lesions.

Disease Parameters

Radiologic Surveillance

Standard of care follow-up post RT will include contrast enhanced MRI and parametric imaging unless clinically contraindicated should include contrast.

Measurement of Response

Measurement of Response Prior to Study Entry

The revised RECIST guideline, v. 1.1. [European J of Cancer. 45: 228-247, 2009] will be used as applicable to the protocol. See

http://ctep.info.nih.gov/protocolDevelopment/docs/recist_guideline.pdf for further details.

Additional definitions beyond the RECIST guidelines specific to this protocol are incorporated to define local control as described below (Eisenhauer 2009). We will evaluate and report RECIST measures minimally at 12 and 24 months post radiation therapy.

Response Criteria: Evaluation of Target Lesions

Complete Response (CR): Disappearance of all target lesions

Partial Response (PR): At least a 30% decrease in the sum of the diameters of target lesions taking as reference the baseline sum diameters

Progressive Disease (PD): At least a 20% increase in the sum of diameters of target lesions, taking as reference the smallest sum on study (includes the baseline sum if that is the smallest on study). The sum must also demonstrate an absolute increase of at least 5 mm. The appearance of new lesion(s).

Stable Disease (SD): Neither sufficient shrinkage to qualify for PR nor sufficient increase to qualify for PD, taking the smallest sum diameters as reference while on study.

3D Lesion Volumes

In addition to RECIST criteria evaluation on follow-up scans, we will report 3 D volumetric data of individual lesions based on pre and post treatment images over time, for comparison to 2 D RECIST measurements (Guio 2012 and Eisenhauer 2009).

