Measurable Disease Measurable lesions are defined as those that can be accurately measured in at least one dimension (longest diameter for non-nodal lesions and short axis for nodal lesions to be recorded) as ≥ 20 mm by chest x-ray, as ≥ 10 mm with CT scan, or ≥ 10 mm with calipers by clinical exam. All tumor measurements must be recorded in millimeters (or decimal fractions of centimeters).

Non-measurable disease All other lesions (or sites of disease), including small lesions (< 5 mm longest diameter) will be considered non-measurable disease. The presence of lymph nodes suspicious for metastatic disease during screening will be defined as an ineligibility criterion.

Target lesions Only a single target lesion which is biopsy positive will be selected for focal therapy and identified as the dominant target lesion and recorded and measured at baseline. Target lesion should be selected on the basis of size (lesions with the longest diameter). We will use T2 weighted MRI image sets with contrast for the baseline measurement.

Non-target lesions All other suspicious lesions should be identified as non-target lesions and should also be recorded at baseline. Measurements of these lesions are not required, but the presence, absence, or in rare cases unequivocal progression of each should be noted throughout follow-up.

Methods for Evaluation of Measurable Disease

All measurements should be taken and recorded in metric notation using a ruler or calipers. All baseline evaluations should be performed as closely as possible to the beginning of treatment. The same method of assessment and technique should be used to characterize the dominant lesion at baseline and during follow-up. Use of 3T MRI T2 scans with contrast is required for the baseline measurement and is the preferred method and technique for all imaging-based evaluations. The mpMRI image data will additionally be recorded, evaluated and reported separately.

Response Criteria

Evaluation of Target lesions

Response	Evaluation of Target Lesions
Complete Response (CR)	Disappearance of all target lesions. Any pathological lymph nodes (whether target or non-target) must have reduction in short axis to < 10 mm.
Partial Response (PR)	At least a 30% decrease in the sum of diameters of target lesions, taking as reference the baseline sum of diameters.

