CR	Not evaluated	No	PR		
PR	Non-CR/Non-PD/not evaluated	No	PR		
SD	Non-CR/Non-PD/not evaluated	No	SD	Documented at least once ≥ 4 wks from baseline **	
PD	Any	Yes or No	PD	No prior SD, PR or CR	
Any	PD ***	Yes or No	PD		
Any	Any	Yes	PD		

* See RECIST manuscript for further details on what is evidence of a new lesion.
 
** Only for non-randomized trials with response as primary endpoint.
 
*** In exceptional circumstances, unequivocal progression in non-target lesions may be accepted as disease progression.
					

Note: Patients with a global deterioration of health status requiring discontinuation of treatment without objective evidence of disease progression at that time should be reported as “symptomatic deterioration.” Every effort should be made to document the objective progression even after discontinuation of treatment.
					

For Patients with Non-Measurable Disease (i.e., Non-Target Disease)

Non-Target Lesion	New Lesions	Overall Response
CR	No	CR
Non-CR/non-PD	No	Non-CR/non-PD *
Not all evaluated	No	Not evaluated
Unequivocal PD	Yes or No	PD
Any	Yes	PD

* ‘Non-CR/non-PD’ is preferred over ‘stable disease’ for non-target disease since SD is increasingly used as an endpoint for assessment of efficacy in some trials so to assign this category when no lesions can be measured is not advised.

RECIST (Eisenhauer 2009) Tumor Response

Tumor measurements will be defined by the PI or treating physician, and confirmed by an objective radiation oncologist or radiologist not associated with this study.

Duration of overall response: The duration of overall response is measured from the time measurement criteria are met for stable disease (SD), partial response (PR) or complete response (CR) - whichever is first recorded, until the first date that recurrent or progressive disease is objectively documented (taking as reference for progressive disease the smallest measurements recorded since the treatment started)

The duration of overall CR is measured from the time measurement criteria are first met for CR until the first date that progressive disease is objectively documented. CR will be reported as unconfirmed CR until a repeat image shows duration of response.

Duration of stable disease: Stable disease is measured from the start of the treatment until the criteria for progression are met, taking as reference the smallest measurements recorded since the treatment started, including the baseline measurements.

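### Duration of overall response starts at stable disease, so a man who never reaches partial or complete response is given a response duration

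*Combined protocol and SAP*

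**What the plan says.** Section 9.2 defines three durations in succession.

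- **Overall response.** The clock is "measured from the time measurement criteria are met for stable disease (SD), partial response (PR) or complete response (CR"), whichever of these comes first, and it runs "until the first date that recurrent or progressive disease is objectively documented".
- **Complete response (CR).** "The duration of overall CR is measured from the time measurement criteria are first met for CR".
- **Stable disease (SD).** "Stable disease is measured from the start of the treatment until the criteria for progression are met".

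The response criteria in the same section set partial response (PR) at "At least a 30% decrease in the sum of diameters of target lesions, taking as reference the baseline sum of diameters" and describe SD as "Neither sufficient shrinkage to qualify for PR nor sufficient increase to qualify for PD". Nothing in section 9.2 or section 10.2 limits the overall-response duration to men who reach PR or CR.

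On timing, section 6.1.1 offers each man up to four further MRIs, timed as follows: "1 during therapy (between the 2nd and 3rd fractionated treatments), at 6 months following the end of radiation therapy, and again at 12 and 24", the last two also counted in months. Section 9.2 commits to RECIST reporting at 12 and 24 months at the least. Section 10.2 promises descriptive RECIST reports and names Kaplan-Meier curves for disease-free survival, local progression and distant failure. It names no analysis of response duration.

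**The concern.** A duration of response should begin when a response is seen. Here the clock can begin with a category that the protocol itself defines as falling short of PR. Two things follow from the wording. A man whose best category is SD is credited with a duration of response. A man who does respond, but is first recorded as SD, has the time before his response added to its duration.

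The two neighbouring definitions show that the clocks were meant to differ: the CR clock starts at CR, and SD has a clock of its own. What is at stake is how one descriptive efficacy figure reads in a single-arm pilot of 12 men, where section 9.0 uses serial MRI together with PSA to look at disease control against historical whole-gland data.

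**Working it through.** The plan states no expected duration of response, so there is no figure to reproduce. The check compares the clock as written with one that starts at first PR or CR, on the protocol's own scan times.

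**Inputs**
- Scan times: one mid-treatment, then 6, 12 and 24 months after radiation (section 6.1.1).
- Minimum RECIST reporting times: 12 and 24 months (section 9.2).
- Start and end of each clock: section 9.2.

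**Assumptions**
- No progression by month 24, so every duration is censored and is a lower bound.
- The man is SD at every classified scan before his first PR or CR.
- The mid-treatment scan, where counted, is taken as month 0.
- All scans are done, although section 6.1.1 lets men decline follow-up MRI and stay on study.

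**Formulas**
- As written: 24 − (month of first SD, PR or CR).
- From response: 24 − (month of first PR or CR); not defined for a man who never reaches either.
- Difference: (month of first PR or CR) − (month of first SD, PR or CR).

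| Scans classified | First PR or CR | As written (months) | From response (months) | Difference (months) |
|---|---|---|---|---|
| 6, 12, 24 | 6 | ≥ 24 − 6 = 18 | ≥ 24 − 6 = 18 | 0 |
| 6, 12, 24 | 12 | ≥ 18 | ≥ 24 − 12 = 12 | 6 |
| 6, 12, 24 | 24 | ≥ 18 | ≥ 24 − 24 = 0 | 18 |
| 6, 12, 24 | never (SD throughout) | ≥ 18 | none | – |
| 12, 24 only | 12 | ≥ 24 − 12 = 12 | ≥ 12 | 0 |
| 12, 24 only | 24 | ≥ 12 | ≥ 0 | 12 |
| 12, 24 only | never (SD throughout) | ≥ 12 | none | – |
| mid, 6, 12, 24 | 6 | ≥ 24 − 0 = 24 | ≥ 18 | 6 |
| mid, 6, 12, 24 | 12 | ≥ 24 | ≥ 12 | 12 |
| mid, 6, 12, 24 | 24 | ≥ 24 | ≥ 0 | 24 |
| mid, 6, 12, 24 | never (SD throughout) | ≥ 24 | none | – |

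**Reading the table**
- The difference is zero whenever PR or CR is the first category recorded, whichever scans count.
- A man with PR at month 12 gains 6 months if month 6 is classified and he was SD then, and nothing if classification starts at month 12.
- A man who is SD throughout always gets a response duration as written (at least 12, 18 or 24 months, depending on which scans count) and none under the alternative.
- The protocol does not say whether the mid-treatment or 6-month scan receives a RECIST category, so the answer depends on a choice it leaves open.

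**The case against.** The best defence is that the measure is a disease-control duration under a poor label. Section 9.0, under the analysis of the primary endpoints, reports response to therapy in four categories, one of which is stable. The tables in section 9.2 list SD in the overall-response column. Section 9.2 also says that definitions beyond RECIST have been added in order to define local control. Read that way, a clock from first non-progression to progression is coherent.

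This supports mislabelled, not correct. Progressive disease stands in the same column, so being listed there does not make a category a response. The item is called duration of overall response, SD already has its own duration, and section 10.2 already plans a time-to-local-progression curve. If disease control was intended, the name still has to change.

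Two stronger readings are tempting, and the documents do not support either.
- A reader might infer that counting the same months under both overall response and SD is itself an error. The durations are never added together. The SD clock runs from the start of treatment to progression, so it overlaps a responder's PR or CR time even after the overall-response definition is corrected.
- A reader might infer that SD means a lesion that never shrinks. SD includes real shrinkage short of 30%, so some men with SD will have smaller lesions. They still do not meet the protocol's own threshold for PR.

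**Conclusion.** The definition is wrong as written, and the consequence is small. It gives a response duration to men whose best category is SD, and it lengthens a responder's duration only when SD is recorded before PR or CR.

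With RECIST classified at 6, 12 and 24 months and no progression by month 24, the illustration is at least 18 months against at least 12 for SD then PR at 12, and at least 18 against no response duration for SD throughout. These are scenarios with censored follow-up, not estimates for this trial.

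A reader might infer that every responder's duration is inflated, or that it is inflated by half (18 against 12). Neither follows. There is no effect when response is recorded first. The ratio compares two lower bounds in one chosen scenario, and the plan gives no expected frequency of SD before PR from which an effect across the cohort could be worked out.

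Nor does the rule distort the trial's efficacy results in general. It leaves the RECIST categories, best overall response, PSA failure and disease-free survival unchanged. Response duration is descriptive, is not a primary endpoint, and drives no sample size or decision rule. The effect stops at that one summary.

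**What to change.** In section 9.2, remove stable disease from the categories that start the overall-response clock. The duration then runs from first PR or CR to documented recurrence or progression, in men who reach PR or CR only, with those not progressed censored at their last scan. Keep the separate duration of stable disease. State which MRI scans receive a RECIST category, in particular whether the mid-treatment and 6-month scans do.

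If a disease-control duration was intended, rename the measure accordingly and do not report it as a duration of response.

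The change deletes a few words and adds a sentence or two, with no extra patients, visits or scans. The cost is that the descriptive figure becomes less favourable and rests on fewer than the 12 men if some never respond.

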10.0 Statistical Plan

10.1 Data Collection

All study-related data will be entered into OnCore. Access will be limited via a password known only to the investigator and designated research personnel (study nurse(s), data manager(s)).

10.2 Statistics

Statistical Considerations

Chi-square and cluster re-sampling analyses will be used to correlate suspicion on multiparametric magnetic resonance imaging and the incidence of cancer detected on biopsy.

The primary goal of this study is to evaluate acute and late toxicities. In addition clinical data will be collected to monitor for tumor control. Digital rectal examination (DRE) and serum prostate antigen (PSA) will be evaluated every 3 months for two years. Toxicity will be evaluated EPIC EQ D5, Sexual Medication, Device Screening Questionnaires completed by the patients or in conversation with the patient by the clinical staff, at baseline, 6, 12 and 24 months following the end of radiation therapy (+/- 14 days). Rates of acute and late side effects and adverse events will be summarized as proportions, with 95% confidence intervals.

Biochemical failure will be based on PSA values using the Phoenix definition (clinical nadir +2ng/mL). Data from all patients will be pooled. Survival rates estimated from the Kaplan-Meier curves will be estimated with 95% confidence intervals. We will also track virtual treatment plans based on standard models for treatment to the whole gland versus partial gland MRI-TPUS validated planning to report change in dosimetric parameters of the focal SBRT versus traditional whole-gland treatment plans for statistical comparison.

Either a positive DRE or rising PSA may be used as clinical indication for additional MRI surveillance. When additional MRI are available, tumor volume will be summarized by mean \pm STD and the difference between two time points (pre and post treatment) will be examined using paired T-test. Radiographic efficacy will be summarized by calculating Kaplan-Meier curves for the following: disease-free survival, time to local progression, time to distant failure. Descriptive reports of RECIST (1.1) and volumetric findings will be provided.

Acute/Late Toxicity and Quality of Life Measurements

Using multivariate analysis, we will report acute and late (>180 days post SBRT) rates of GI toxicity with dose-volume histogram. We will also report time to event analyses collected for all available HRQOL data collected.

Temporal pattern of quality of life scores will be summarized graphically; and repeated measures analysis of variance (ANOVA) will be conducted to test for changes in scores over time. The predictive value of demographic, pathological and clinical factors on the scores will be examined by mixed models assuming missing values are missing at random.

Sample Size

Twelve patients will be evaluated in this pilot study. As a proof-of-principle study, it's not design to have the appropriate power (80%) for detecting significant difference in clinic outcomes (i.e.

toxicities, survival or QOL), but to provide some preliminary data for future studies. A sample of 12 patients, however, achieves 78% power to detect 8% difference of urinary toxicity against historical controls under whole gland therapy using a two-sided binomial test with the target significance level of 0.2. We anticipate that a minimum of twenty four patients will be screened leading to twelve patients who will be treated and evaluated on-study in this pilot study.

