5.1 Early Withdrawal of Subjects

Criteria for Removal from Study

Subjects may be removed from the study upon request or at the discretion of the Principal Investigator for safety reasons, failure of subject to adhere to protocol requirements, subject consent withdrawal, or disease progression. Withdrawn subjects may be replaced.

Follow-up for Withdrawn Subjects

Subjects may withdraw from the study at any point. If subjects withdraw prior to delivery of SBRT, they may be replaced with an additional subject(s). Follow up for withdrawn subjects will continue per standard of care for disease stage as reported through the staging biopsy, off study. All routine standard of care imaging and physical exams to monitor disease progression, may be conducted as similar to that care described on trial. Data collected following consent and registration through the screening biopsy will be reported for all subjects, including those withdrawn prior to SBRT.

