7.2 Study Visits

Biopsy and Fiducial Placement – visit #2

- Weight
- Vitals including blood pressure, pulse, respiratory rate, temperature
- Physical examination
- Guided biopsy
- Fiducial placement

MRI and CT scans for RT SIM – visit #3

- RT CT (with contrast unless contraindicated) for simulation
- Pelvic MRI with Contrast
- Pelvic CT for SIM

SBRT #1 – visit #4

- RT treatment

SBRT #2 – visit #5

- RT treatment

MRI – visit #6

- Pelvic mpMRI with Contrast

SBRT #3 – visit #7

- Adverse events assessment (may be completed by telephone call within 7 days post visit 7)
- RT treatment

Follow up, every 3 months for up to 24 months – visits #8 - #16

- Weight
- Vitals including blood pressure, pulse, respiratory rate, temperature
- Physical examination
- ECOG performance status
- Quality of life Score standard of care IPSS and SHIM Scores
- Adverse events assessment

Post SBRT Follow up Measurements

- PSA to be completed at ALL follow up visits

- DRE to be completed at **ALL** follow up visits
- Serum Creatinine and BUN Blood Draw at **6, 12, and 24** months follow up prior to MRI
- Pelvic MRI to be completed at **6, 12, and 24** month follow up visits with contrast
- EPIC EQ D5, Sexual Medication/Device screening to be completed at **6, 12 and 24** months

Any positive results for staging Post RT (positive digital rectal exam or evidence of biochemical failure using the clinical nadir +2 definition (serum PSA rise above 2ng/mL from the post therapy nadir (Phoenix, Abramowitz 2007) may trigger clinical indication for SOC staging MRI to rule out disease progression. If acquired, this data will be collected for comparison to other serial MRI data. Should a patient be deemed to have failed therapy using the Phoenix criteria (nadir +2ng/mL PSA) the subject/s will be referred for consultation for review of options for salvage therapy, and if the patient elects a second treatment the subject will be taken off study.

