9.1 Safety and Efficacy Endpoints

Assessment of early clinical outcomes in focal SBRT for low risk prostate cancer patients. Twenty-four hormone naïve low to intermediate risk prostate cancer patients will be screened for PSA level, acute toxicities and quality of life (QOL) measures at baseline and twelve will be followed at longitudinal follow-up appointments.

Acute and Late GI and GU Adverse Events (AEs)

Adverse events are evaluated by the CTEP Active Version of the NCI Common Terminology Criteria for Adverse Events (CTCAE). We will record in Oncore the highest grade reported during a reporting period. The treatment-related attribution includes definitely, probably or possibly related to treatment. An acute adverse event is defined as the first occurrence of worst severity of the adverse event ≤ 30 days after the completion of RT. We will evaluate the acute radiation therapy-related adverse events. Specifically, we are interested in the percentage of acute GI and GU Grade 3+ adverse events that may occur, which is considered to be similar to the high RT dose arm of RTOG 0126 in terms of RT dose. If our partial prostate hypofractionated regimen has an acceptable percentage, then it will be deemed to have an acceptable adverse event profile. We will report the percentage for the regimen as well as the one-sided 97.5% confidence interval. For example, the number of patients in the high dose arm of RTOG 0126 Phase II reported that 1% of patients experienced Grade 3+ GI/GU acute toxicity, with no patient experiencing Grade 4 or 5 toxicities (citation) should be greater than this pilot study. A late adverse event is defined as the first occurrence of worst severity of adverse event > 180 days after RT completion. Late Grade 3+ GU/GI toxicity information will be collected and reported also.

PSA Failure

Failure occurs when the PSA is first noted to be 2 ng/mL or more than the patient's nadir value post RT completion (Phoenix, Abramowitz 2009). PSA failure at 6, 12 and 24 months following RT will be estimated for the series by the cumulative incidence method (Gray 1988). Also, confidence intervals will be reported.

Disease-Free Survival (DFS)

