The disease-free survival duration will be measured from the date of treatment to the date of documentation of disease progression or until the date of death from any cause. DFS at 6, 12 and 24 months for each patient and the series by the Kaplan-Meier method (Kaplan 1958). Also, 95% confidence intervals will be reported.

Analysis for Endpoints Related to HRQOL

We will use three instruments to measure HRQOL: the Expanded Prostate Cancer Index Composite (EPIC), the Utilization of Sexual Medications/Devices, and EQ-5D. Protocol eligible patients will be included in the HRQOL analysis only if they have provided baseline and at least one subsequent measurement. All HRQOL instruments (EPIC, the Utilization of Sexual Medications/Devices and EQ-5D) will be collected on all cases participating in the trial. The standard departments QOL instruments may also be used to report outcomes with both the International Prostate Symptom Score (IPSS) and Sexual Health Information Measurement (SHIM) obtained from chart review.

The EPIC Supplement Utilization of Sexual Medications/Devices, and EQ-5D will be collected at pretreatment (baseline) and at 6, 12 and 24 months after radiation therapy ends. Patient self-assessment of symptoms will be performed using four primary EPIC scales: urinary, bowel, hormonal and sexual symptoms. The Utilization of Sexual Medications/Devices and EQ-5D Questionnaires are found in Appendix 3.

For all primary HRQOL analyses we will estimate the degree of change from baseline to 6, 12 and 24 months as continuous variables. For this endpoint, in each domain, the actual change score will be used as the statistic and a t-test will be used to evaluate if the change is different from 0. Confidence intervals also will be computed

The primary objective in HRQOL analysis is to estimate the change from baseline to 24 months. The response will be the change of measurement from baseline to 24 months (or the last available HRQOL data point where data are missing). The one-sample t-test will be used to test the null hypothesis that response change is 0. For the regimen to maintain the overall significance level for testing three HRQOL instruments. In addition, we will describe the distributions of HRQOL data collection patterns over all collection points in each treatment arm.

Demonstrate dosimetric and biological advantage of focal SBRT versus whole-gland therapy

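### Kaplan-Meier for time to local progression and time to distant failure overstates incidence if death or off-study salvage is censored; cumulative incidence is already in the plan for PSA failure

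*Combined protocol and SAP*

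**What the plan says.** The plan uses two estimators for its failure endpoints.

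- Section 10.2, radiographic endpoints: "Radiographic efficacy will be summarized by calculating Kaplan-Meier curves for the following: disease-free survival, time to local progression, time to distant failure".
- Section 9.1, PSA failure: "PSA failure at 6, 12 and 24 months following RT will be estimated for the series by the cumulative incidence method (Gray 1988".
- Section 9.1, disease-free survival: the time runs "to the date of documentation of disease progression or until the date of death from any cause", and is estimated by Kaplan-Meier.

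Two provisions can end a man's observation before local or distant failure is seen. Under section 7.2, a man with biochemical failure is referred to discuss salvage, and "if the patient elects a second treatment the subject will be taken off study". Section 5.1 lists, among the grounds on which a subject may be removed, "subject consent withdrawal, or disease progression".

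Section 9.2 gives RECIST criteria for progressive disease. No section defines time to local progression or time to distant failure as time-to-event endpoints. None gives a censoring rule for them, or says how death, salvage treatment or an earlier failure of another kind is handled.

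**The concern.** Kaplan-Meier fits disease-free survival because death is part of the endpoint. Local progression and distant failure are different: a man can die, or leave for salvage treatment, without having had the event. Usual Kaplan-Meier practice censors such a man, which assumes that his later risk equals that of the men still followed. A man who has died has no later risk. A man who left because his PSA rose and he chose further treatment is unlikely to resemble those who stayed. One minus Kaplan-Meier then describes a setting in which these exits do not happen, and it is at or above the proportion of treated men in whom the event is observed before such an exit.

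The plan already uses the method that avoids this, but only for PSA failure. The failure rates from this pilot would therefore sit on different scales, with no reason given. Section 9.0 intends PSA and serial MRI results to be set against historical whole-gland data, and section 10.2 says that the study is to supply preliminary data for later studies. Both uses need failure rates whose meaning is stated.

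**Working it through.** The documents state no rate for local progression, distant failure or competing events, so there is no plan figure to reproduce. The check sizes the difference under assumed event patterns.

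**Inputs from the documents.** Sample size: "Twelve patients will be evaluated in this pilot study" (section 10.2). Follow-up is 24 months with visits every 3 months (section 7.2), and post-treatment MRI is at 6, 12 and 24 months (sections 6.1 and 7.2).

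**Assumed.** The number and timing of events and competing events; all other men followed to 24 months; competing events censored in the Kaplan-Meier calculation.

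**Formulas.** With d events of interest among n men at risk at each event time:
- 1-KM = 1 − product of (1 − d/n), where men with a competing event simply leave n.
- Cumulative incidence = sum of S × d/n, where S is the proportion free of both kinds of event just before that time. With full follow-up otherwise, this equals events/12.

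| Events (month) | Competing events (month) | 1-KM | Cumulative incidence | Difference (points) |
|---|---|---|---|---|
| 1 (24) | none | 1/12 = 8.3% | 8.3% | 0 |
| 1 (24) | 1 (12) | 1/11 = 9.1% | 8.3% | 0.8 |
| 1 (24) | 2 (9, 12) | 1/10 = 10.0% | 8.3% | 1.7 |
| 1 (24) | 3 (6, 9, 12) | 1/9 = 11.1% | 8.3% | 2.8 |
| 2 (12, 24) | 1 (9) | 1 − (10/11)(9/10) = 18.2% | 16.7% | 1.5 |
| 2 (12, 24) | 2 (9, 15) | 1 − (10/11)(8/9) = 19.2% | 16.7% | 2.5 |
| 2 (12, 24) | 3 (9, 15, 18) | 1 − (10/11)(7/8) = 20.5% | 16.7% | 3.8 |
| 1 (12) | 1 (18) | 1/12 = 8.3% | 8.3% | 0 |

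The first and last rows show the condition: the difference is zero with no competing event, and also when the only competing event comes after the last event of interest.

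**Largest gap for a given count.** If c competing events all precede two progressions, 1-KM = 2/(12 − c). For c = 3 this is 2/9 = 22.2% against 2/12 = 16.7%, a gap of 5.6 points.

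**Constant hazards.** Take h = −ln(1 − net 24-month risk)/24 for each cause, and cumulative incidence = h1/(h1 + h2) × (1 − exp(−24(h1 + h2))). For net risks of 5% to 20% (event) and 2% to 30% (competing), the overstatement runs from 0.05 points (5% and 2%) to 3.1 points (20% and 30%: 20.0% against 16.9%).

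**Sampling error for scale.** The exact 95% interval is 0.2% to 38.5% for 1/12 and 2.1% to 48.4% for 2/12.

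**The case against.** The strongest reply is that the plan never says these men will be censored. It also speaks of Kaplan-Meier curves, not of one minus Kaplan-Meier reported as an incidence. Competing events may be few: the men are ECOG 0 or 1, severe active comorbidity is excluded, and follow-up is 24 months, so deaths should be uncommon. Leaving for salvage requires the man to choose a second treatment, and removal for progression is discretionary. The endpoints are descriptive, and section 10.2 says that the study is not designed to have adequate power for clinical outcomes. No decision rule, alpha or sample size depends on these curves.

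All of this stands as a limit on size. It does not remove the gap: with no rule stated, censoring is what an analyst would do by default, and the salvage route out of the study is written into the protocol and tied to biochemical failure.

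Three stronger readings are tempting, and the documents do not support them.

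- *A reader might infer that the two estimates are certain to be biased upward.* They are not. The overstatement needs censoring of competing events and an event of interest after one of them.
- *A reader might infer that PSA failure has two estimators, leaving room to choose after seeing the data.* Section 10.2 does say "Survival rates estimated from the Kaplan-Meier curves will be estimated with 95% confidence intervals" soon after defining biochemical failure. But a sentence on pooling stands between, survival rates most naturally means disease-free survival, and section 9.1 is explicit about PSA failure. At most, a clarifying phrase would help.
- *A reader might infer that any earlier failure of another kind should count as a competing event.* Local progression does not preclude distant failure, and PSA failure precludes neither. Under section 7.2 a PSA rise may prompt the MRI on which progression is found. Counting PSA failure as competing would drop those progressions and change the endpoint to site of first failure.

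**Conclusion.** The point holds in a conditional form and is minor. If death without the event and departure for salvage treatment are censored, 1-KM for local progression and distant failure is never below cumulative incidence, and exceeds it whenever an event of interest follows such an exit. Within the assumed patterns the excess is a few percentage points at most, well inside the sampling error of 12 men.

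The direction of any error is a property of the estimators and does not depend on the assumed counts. The size does, because the documents give no rates. The case for acting is that any error goes one way, is avoidable, and can be removed with a method the plan already names.

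**What to change.** In section 10.2:

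1. Define time to local progression and time to distant failure (start date, event, end of observation).
2. Estimate both by the cumulative incidence method already named in section 9.1, with confidence intervals. Treat death without the event and off-study salvage treatment as competing events.
3. Do not treat PSA failure, or failure at the other site, as a competing event while the man remains under observation.
4. Keep Kaplan-Meier for disease-free survival.
5. Optionally, add that PSA failure is reported by the section 9.1 method.

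The cost is a few sentences of analysis text, with no new data, visits or patients. One consequence should be stated openly: with salvage as a competing event, the estimate is the incidence of local or distant failure before any second treatment, and should be labelled so.
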